11.2.2. Resumption of Study Treatment Dosing

Resumption of study treatment is to be considered on a case-by-case basis and must be discussed with the Medical Monitor. However, subjects who have abnormal laboratory values, as described in Table 3, sustained on 3 consecutive occasions (i.e., for more than 4 consecutive weeks) must permanently discontinue study treatment (Section 10.1). Subjects who have temporarily withheld BG00012 due to lymphopenia may resume BG00012 according to Section 11.3.

Subjects with abnormal laboratory values after Week 12 (after which clinic visits occur once every 3 months), who are allowed to resume study treatment dosing following a 2- to 4-week interruption, will restart dosing at a reduced dose for 1 week. Subjects must also return to the initial every-4-week visit schedule for safety assessments (see Table 1) for 2 consecutive normal laboratory assessments before reverting to the every-3-month schedule. Subjects will take 120 mg BID for 1 week. After 1 week at the reduced dose, subjects will take 240 mg BID.

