11.2.3. Subsequent Development of Additional Laboratory Abnormalities

Subjects who develop a subsequent abnormal value for the same laboratory parameter at any other time during the study must permanently discontinue dosing with study treatment, i.e., only 1 dosing interruption is allowed for each subject for the same laboratory abnormality. However, subjects who subsequently experience an abnormality of a different laboratory parameter can have study treatment withheld again. For example, if a subject had dosing temporarily withheld for an abnormal ALT/SGPT, then had dosing resumed after ALT/SGPT returned to acceptable limits, and subsequently developed abnormal white blood cells (WBCs), the subject may have

CONFIDENTIAL

The information contained herein may not be used, disclosed, or published without the written consent of Biogen MA Inc.

study treatment withheld again. However, only 2 dosing interruptions are allowed for each subject.

Any subject who experiences abnormal laboratory results that meet the criteria defined in [Table 3](#) on a third occasion must permanently discontinue dosing.

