Subjects who temporarily withhold study treatment due to decreases in lymphocyte count, as described in [Table 4](#), may resume study treatment when lymphocyte counts recover (defined as a lymphocyte count \geq LLN on 2 consecutive occasions at least 4 weeks apart). If the lymphocyte count is $<500/\text{mm}^3$ on 1 occasion (confirmed by repeat testing) on resumption of study treatment, then study treatment must be permanently discontinued. Subjects who discontinue study treatment due to lymphocyte count $<500/\text{mm}^3$ should continue tests and assessments according to the schedule defined in Section 4 until the lymphocyte count recovers or until the final Follow-Up Visit (whichever is sooner). Subjects whose lymphocyte counts remain $<\text{LLN}$ at the end of the study (Week 96) will complete the final Follow-Up Visit and then be followed outside of this study at the Investigator's discretion.

See [Figure 2](#) for the treatment schedule of subjects with lymphocyte counts $<500/\text{mm}^3$.

CONFIDENTIAL

The information contained herein may not be used, disclosed, or published without the written consent of
Biogen MA Inc.

Figure 2: Schedule for Subjects With Lymphocyte Count <500/mm³

LLN = lower limit of normal.

CONFIDENTIAL

The information contained herein may not be used, disclosed, or published without the written consent of
Biogen MA Inc.

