5.3.3 Lymphocyte analysis during lymphocyte follow-up period

Subjects who temporarily withhold, or permanently discontinue study treatment for any reason and have a lymphocyte count <LLN will continue protocol-required visits and assessments and will also be followed up every 4 weeks for 24 weeks, then every 12 weeks (unless clinically indicated more often or at the Investigator's discretion) until the lymphocyte count is \geq LLN or for up to 48 weeks following drug discontinuation, whichever occurs sooner.

In general, the lymphocyte follow-up analysis will include subjects who have at least one ALC < LLN during the treatment period and have at least one ALC value during the lymphocyte follow-up period. The lymphocyte follow-up period is defined as the time starting from the date of temporary dose interruption or study drug discontinuation. The start date of the lymphocyte follow-up period is defined as the start date of temporary dose interruption or the treatment end date. The last observed value collected on or prior to the date of temporary dose interruption or study drug discontinuation will be the reference point (lymphocyte follow-up baseline). Data that are collected during the lymphocyte follow-up period will be assigned to an appropriate visit by using the mid-point of the two visits windowing scheme. Visits will be mapped every 4 weeks for 24 weeks and then every 12 weeks afterward. The detailed windowing rule is available in [Appendix 2](#). Patients who have any post lymphocyte follow-up baseline values will be included in the analysis. ALCs collected during the lymphocyte follow-up period will be analyzed. The lymphocyte subsets and Ig isotypes observed obvious decline over time in the treatment period will also be explored.

The by-visit summary of actual value, change and percent change from the lymphocyte follow-up baseline in ALC during the lymphocyte follow-up period will be presented. The by-visit summary of actual value, change and percent change from the study baseline in ALC during the whole study period will also be presented. In addition, graphical display of median (Q1/Q3) of actual value in ALC in the whole study period will be presented; graphical display of median (Q1/Q3) of percent change from study baseline and lymphocyte follow-up baseline will be presented. The same analyses will be applied to selected lymphocyte subsets and Ig isotypes of interest.

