5.4.6 Safety analysis during lymphocyte follow-up period

[figure not shown]
The concomitant medication, AEs, hematology, vital signs and physical examination data collected during the lymphocyte follow-up period will be analyzed.

The concomitant medication and AEs, either started prior to the lymphocyte follow-up period and continued during the lymphocyte follow-up period, or started on or after the lymphocyte follow-up period will be listed.

Hematology, vital signs and physical examination data during the lymphocyte follow-up period will either be descriptively summarized or listed. The windowing rule defined in [Section 5.3.3](#) will be used for visit mapping. Additional safety analyses during lymphocyte follow-up period may be conducted.

[figure not shown]
CONFIDENTIAL

The information contained herein may not be used, disclosed, or published without the written consent of Biogen Idec MA Inc.

CONFIDENTIAL

The information contained herein may not be used, disclosed, or published without the written consent of
Biogen Idec MA Inc.

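### SAP 5.3.3 gives the lymphocyte follow-up period a start but no end, so values taken after BG00012 is resumed are tabulated as weeks since stopping

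*SAP*

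**What the plan says.** SAP 5.3.3 defines the analysis period by its start: "The lymphocyte follow-up period is defined as the time starting from the date of temporary dose interruption or study drug discontinuation". It then gives the start as a date: "The start date of the lymphocyte follow-up period is defined as the start date of temporary dose interruption or the treatment end date". To enter the analysis a subject needs at least one ALC below LLN during treatment "and have at least one ALC value during the lymphocyte follow-up period". Data in the period are mapped to visits by date, using the follow-up windows in Appendix 2. There are eight; the last runs from Day 295 with no upper bound.

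The section opens by restating the visit schedule: extra visits continue until ALC is back at LLN "or for up to 48 weeks following drug discontinuation, whichever occurs sooner". Resumption of drug is not mentioned.

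SAP 5.4.6 uses the same period for safety. Medications and adverse events that began earlier and continued into it, "or started on or after the lymphocyte follow-up period will be listed".

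The protocol provides for restarting. Section 11.2.2 covers subjects with abnormal laboratory values after Week 12 "who are allowed to resume study treatment dosing following a 2- to 4-week interruption", and puts them back on four-weekly visits until two consecutive normal laboratory assessments. Under 11.3.1, subjects withheld for low lymphocytes "may resume study treatment when lymphocyte counts recover", which requires two values at or above LLN at least 4 weeks apart. Section 11.2.3 says "only 2 dosing interruptions are allowed for each subject". Routine visits go on to Week 96.

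**The concern.** These tables and plots are meant to show what happens to ALC and lymphocyte subsets once the drug is stopped. In the visible SAP they are the only planned summary of that. Protocol 5.3.2 links progressive multifocal leukoencephalopathy to prolonged lymphopenia, so readers will look to them for recovery.

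Under the rule as written, a value labelled 24 weeks from follow-up baseline need not come from a subject who is 24 weeks off drug. The subject may have been off for 4 weeks and back on for 20. The tables would mix the two states without showing it. Two programmers could also index the same sample to different stops, because nothing says which stop counts.

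**Working it through.** **Step 1. Reproduce the windows.** Inputs: the Appendix 2 follow-up targets, Days 29, 57, 85, 113, 141, 169, 253 and 337. Each window should start at the mid-point with the previous target: (29+57)/2 = 43, (57+85)/2 = 71, (85+113)/2 = 99, (113+141)/2 = 127, (141+169)/2 = 155, (169+253)/2 = 211, (253+337)/2 = 295. With the first window starting at Day 2, this gives 2–42, 43–70, 71–98, 99–126, 127–154, 155–210, 211–294 and 295 onward. All eight match Appendix 2. Only the last has no end.

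**Step 2. Follow one subject.** Take a subject with at least one ALC below LLN on treatment who has a 4-week hold for a Table 3 laboratory value (a liver enzyme, say). The stop is Day 169; dosing resumes on Day 197. Follow-up day = study day − 169 + 1. Weeks back on drug = (study day − 197)/7. Routine study days are the Appendix 2 targets. The Day 225 visit assumes the four-weekly schedule of Protocol 11.2.2 is counted from resumption.

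| Visit | Study day | Follow-up day | Follow-up window | Weeks back on drug |
|---|---|---|---|---|
| Four-weekly visit | 225 | 57 | 8 weeks (43–70) | 4 |
| Week 36 | 253 | 85 | 12 weeks (71–98) | 8 |
| Week 48 | 337 | 169 | 24 weeks (155–210) | 20 |
| Week 60 (CBC only) | 421 | 253 | 36 weeks (211–294) | 32 |
| Week 72 | 505 | 337 | 48 weeks (295 on) | 44 |

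Routine CBCs alone fill four windows, and the Day 225 visit makes at least five of eight for ALC. Weeks 84 and 96 (follow-up Days 421 and 505) also land in the open last window; the closest-to-target rule in SAP 5.1 keeps Week 72. For subsets, Week 60 has no sample, so routine samples fill three windows (12, 24 and 48 weeks).

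**Step 3. How much of the grid is exposed.** Count the windows that lie wholly after resumption:
- Hold of 2 to 4 weeks, resuming on follow-up Day 15 to 29: seven of eight (from Day 43).
- Lymphopenia hold with ALC at or above LLN at follow-up Weeks 4 and 8, resuming on Day 57: six of eight (from Day 71).
- Lymphopenia hold with ALC at or above LLN at Weeks 20 and 24, resuming on Day 169: two of eight (from Day 211).

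These are windows where an on-drug value could fall, not windows that must be filled.

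**Step 4. The start date.** Any subject who resumes has at least two candidate starts, the interruption and the later treatment end. Two interruptions plus treatment end make three. With holds starting on Days 169 and 400, the Day 421 CBC is follow-up Day 421 − 169 + 1 = 253 (36-week window) or 421 − 400 + 1 = 22 (4-week window).

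**Step 5. A cap consistent with the SAP.** The hematology Week 48 window has the same target, Day 337, and the next target is Day 421. The mid-point is (337+421)/2 = 379, so that window closes at Day 378. The distance is symmetric: 337 − 295 = 42 and 379 − 337 = 42.

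**The case against.** The best answer is that SAP 5.3.3 does contain a limit: it opens with follow-up until LLN or 48 weeks, and a later cross-reference speaks of follow-up visits. If that limit is the analysis period, a lymphopenia hold closes before resumption, because the first value at LLN ends the extra visits and resumption needs two. This stands in part. Such subjects would normally have left the extra visits before restarting, so lymphopenia holds are not the main source. But the opening text says how long extra visits are scheduled. The operative sentences define the period by its start and take data by date, the 48-week limit is not carried into the last window, and resumption is never an end point. Routine visits after a restart therefore still qualify.

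A reader might infer that reported recovery shrinks in proportion to the on-drug share, for example to 75% of the true value if a quarter of a window's values are on drug. The documents do not support that size. It assumes no change from follow-up baseline once back on drug, and no share is given. After a lymphopenia hold, a confirmed count below 500/mm³ on resumption requires permanent discontinuation, so continuing on-drug values will generally lie above that baseline. The arithmetic also applies to means, whereas the planned plots show medians.

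A reader might also infer that the primary analysis is wrong because SAP 5.1 lets off-drug samples into the main windows. They can enter: with a last dose on Day 280, the Follow-Up Visit on Day 280 + 28 = 308 falls in the Week 48 subset window (295–420). But using all observed data is a stated and defensible choice, and subjects may remain in the study off drug. That supports an optional sensitivity run, not a finding of error.

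**Conclusion.** The point holds for the follow-up analysis. Applied literally, SAP 5.3.3 and Appendix 2 tabulate on-drug values as weeks since stopping, and they do not fix the start date for a subject with more than one stop. The exposure comes mainly from short non-lymphopenia holds and routine visits in subjects with at least one ALC below LLN on treatment.

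In the worked case at least 5 of 8 ALC windows can hold on-drug values. That describes one hypothetical subject and rests on the visit timing assumed there; it is not a study-wide magnitude. How many subjects interrupt and resume is not given. The direction is probably toward understating recovery, since Protocol 5.3.2 reports a mean fall in lymphocytes of about 30% after a year on drug. The size is not shown.

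The affected outputs are descriptive and serve no visible primary or secondary endpoint, so the main results are not at risk. Parts of the SAP are blacked out, so statements about what is absent refer to the visible text. The correction is nearly free and should be made.

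**What to change.** In SAP 5.3.3:
- End each follow-up period at the earliest of BG00012 resumption, 48 weeks after the stop (with the visit-window allowance), or last visit.
- Cap the last Appendix 2 follow-up window, for example Day 295 to 378, to match the hematology Week 48 window.
- Either open a new period at each stop or name the index stop, and fix the choice before the tables are run.
- Apply the same end to the safety outputs in SAP 5.4.6.

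This takes a few sentences and a date condition in the programs, with no new data and no change to how subjects are managed. The downside is fewer values in the late follow-up windows: the subject in Step 2 would contribute to the 4-week window at most.

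Optional, for the main by-visit analyses: keep the all-observed analysis as the main one, report the number of off-treatment samples at each visit from the dosing dates already used in SAP 5.2.5, and add an on-treatment sensitivity run. That run would informatively exclude subjects withheld for lymphopenia, so it should be labelled as a sensitivity analysis and not replace the main one.

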DMF was generally well tolerated and demonstrated an acceptable safety profile. The most common AEs associated with DMF were flushing and gastrointestinal (GI) events. In subjects who experienced these types of events, the events were generally mild or moderate in intensity, tended to decrease in incidence after the first month, and only infrequently led to treatment discontinuation. There are a number of potential management strategies for these side effects. In the Phase 2 and 3 controlled and uncontrolled clinical studies in subjects with RRMS, BG00012 treatment was associated with a gradual decrease from baseline in mean leukocyte counts driven primarily by decreases in mean lymphocyte counts; mean lymphocyte counts decreased by approximately 30% of their baseline value after 1 year and then plateaued and remained stable through more than 6 years of follow-up. While decreases in lymphocyte counts have been observed with BG00012 treatment, in the placebo controlled Phase 2 and 3 studies BG00012 was not associated with an increased risk of infection, serious infection, or opportunistic infection compared with placebo. However, in the long-term extension study (109MS303), progressive multifocal leukoencephalopathy (PML) has occurred in the setting of severe, prolonged lymphopenia following BG00012 administration. PML has also been reported in the postmarketing setting in the presence of prolonged moderate to severe lymphopenia. The majority of all cases occurred in patients with lymphocyte counts $<0.5 \times 10^9/L$. With open-label

CONFIDENTIAL

The information contained herein may not be used, disclosed, or published without the written consent of
Biogen MA Inc.

and marketed use of BG00012, there has been no other evidence of an increased risk of infections, serious infections, or opportunistic infections.

See the Investigator's Brochure for detailed information on clinical studies.

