11.3.2. Schedule for Subjects With Lymphocyte Counts <LLN to $\geq 500/\text{mm}^3$

Subjects with lymphocyte count <LLN to $\geq 500/\text{mm}^3$ will have tests and assessments according to the schedule defined in Section 4. If these subjects complete, temporarily withhold, or permanently discontinue study treatment for any reason, they will be followed as described in Section 11.3.3.

11.3.3. Schedule for Subjects Who Temporarily Withhold or Permanently Discontinue Study Treatment for Any Other Reason Than Lymphopenia and Have a Lymphocyte Count <LLN

[figure not shown]
Subjects who temporarily withhold or permanently discontinue BG00012 for any other reason than lymphopenia (see Section 11.2) and who have a lymphocyte count <LLN will be followed every 4 weeks for 24 weeks, then every 12 weeks (**unless clinically indicated more often or at the Investigator's discretion**) until the lymphocyte count is $\geq \text{LLN}$ or for up to 48 weeks following drug discontinuation, whichever occurs sooner. Subjects who temporarily withhold or permanently discontinue study treatment and have a lymphocyte count <LLN for 48 weeks should continue tests and assessments according to the schedule defined in Section 4 until the lymphocyte count recovers or until the final Follow-Up Visit (whichever is sooner). Subjects whose lymphocyte counts remain <LLN at the end of the study (Week 96) will complete the final Follow-Up Visit and will then be followed up outside of this study at the Investigator's discretion.

See [Figure 3](#) for a schedule of subjects who complete, temporarily withhold, or permanently discontinue BG00012 for any other reason and who have a lymphocyte count <LLN.

CONFIDENTIAL

The information contained herein may not be used, disclosed, or published without the written consent of
Biogen MA Inc.

Figure 3: Schedule for Subjects Who Temporarily Withhold or Permanently Discontinue Study Treatment for Any Other Reason Than Lymphopenia* and Have Lymphocyte Count <LLN

LLN = lower limit of normal.

*For subjects with low lymphocytes, refer to Section 11.3.1 and 11.3.2.

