5.3.1 Analysis of the Primary Endpoint

The primary endpoints are the changes in lymphocyte subset counts for up to 48 weeks. The actual value, change and percent change from baseline in count and percent for each lymphocyte subset will be descriptively summarized at each applicable visit. Graphical display of median (Q1-25 percentile/Q3-75 percentile) of actual value and percent change from baseline in count and percent for each lymphocyte subset over time will also be presented. The Wilcoxon signed rank test will be used to test if the change and percent change from baseline in count and percent for each lymphocyte subset is different from zero. Listings of lymphocyte subsets will also be presented.

Furthermore, the primary endpoints will be summarized in various ALC subgroups to evaluate the nature of change in each subset in relation to the change in ALC.

ALC subgroups of interest include (1) subjects who have all ALC values \geq LLN ($0.91 \times 10^9/L$) up to Week 48, and (2) subjects who have at least 1 ALC value $<$ LLN over 48 weeks. A mixed model for repeated measures (MMRM) will be used to estimate the difference between ALC subgroups at each post-baseline visit up to Week 48. The model will be fitted with the change from baseline in count up to Week 48 for each of the TBNK lymphocyte subset as the dependent variable and will include ALC subgroup (all ALC values

CONFIDENTIAL

The information contained herein may not be used, disclosed, or published without the written consent of Biogen Idec MA Inc.

	Protocol 109MS310 An Open-Label Study to Assess the Effects of BG00012 on Lymphocyte Subsets in Subjects With RRMS	Final Version 1.0
---	---	--------------------------

\geq LLN up to Week 48; at least 1 ALC value $<$ LLN over 48 weeks), visit, corresponding Baseline counts, age, gender, and ALC subgroup-by-visit interaction as fixed effects. An unstructured variance-covariance matrix structure will be used in the MMRM model. Least squares (LS) mean, standard error, LS mean difference, 2-sided 95% confidence intervals (CIs) and p-values will be reported. Before the MMRM analysis, appropriate transformation may be performed based on the distribution of each TBNK lymphocyte subset parameter. The same analysis may be applied to other subsets.

Additional subgroups based on ALC values over time are defined:

- 1) ALC $< 0.5 \times 10^9/L$ for ≥ 6 months (24 weeks);

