The concomitant medication, AEs, hematology, vital signs and physical examination data collected during the lymphocyte follow-up visits will be discussed in [Section 5.4.6](#).

Additional analyses exploring lymphocyte subsets and ALCs collected during the lymphocyte follow-up period may be conducted.

CONFIDENTIAL

The information contained herein may not be used, disclosed, or published without the written consent of Biogen Idec MA Inc.

	Protocol 109MS310 An Open-Label Study to Assess the Effects of BG00012 on Lymphocyte Subsets in Subjects With RRMS	Final Version 1.0
---	---	--------------------------

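### SAP 5.3.3 pools off-drug ALC over all starting depths, so where subjects who stopped below 0.5 × 10^9/L are a minority the median can sit near LLN whether or not they recover

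*SAP*

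**What the plan says.** SAP 5.3.3 admits "subjects who have at least one ALC < LLN during the treatment period and have at least one ALC value during the lymphocyte follow-up period". Its follow-up baseline is the last value on or before the interruption or discontinuation. One planned output is "The by-visit summary of actual value, change and percent change from the lymphocyte follow-up baseline in ALC during the lymphocyte follow-up period". A second by-visit table uses the study baseline. Plots follow: "graphical display of median (Q1/Q3) of actual value in ALC in the whole study period will be presented", plus median (Q1/Q3) plots of percent change from each baseline. The same is planned for selected subsets and Ig isotypes. No output is split by ALC at stopping or by reason for stopping, and no count or proportion reaching LLN is specified. The section ends with an option: "Additional analyses exploring lymphocyte subsets and ALCs collected during the lymphocyte follow-up period may be conducted".

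Two routes lead into this period. Protocol 11.3.1 withholds treatment when ALC stays below 500/mm³ (0.5 × 10^9/L) for more than 24 weeks. Protocol 11.3.3 covers a different group: "Subjects who temporarily withhold or permanently discontinue BG00012 for any other reason than lymphopenia" and with a count below LLN.

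Elsewhere the SAP does separate by depth. In 5.3.1, "Additional subgroups based on ALC values over time are defined", with cut-points at 0.5 and 0.8 × 10^9/L and at LLN (0.91). They are applied to the lymphocyte-subset summaries, and 5.4.1 summarises infections by subgroups of ALC over time.

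**The concern.** Recovery means something different at each starting depth. A subject who stops at 0.88 needs a trivial rise to reach LLN; one who stops at 0.40 must more than double. A single median over both describes whichever kind is more numerous at that visit.

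The deep end matters on the protocol's own account. Protocol 5.3.2 describes PML in severe, prolonged lymphopenia and, after marketing, in prolonged moderate to severe lymphopenia, and adds "The majority of all cases occurred in patients with lymphocyte counts" below 0.5 × 10^9/L. A reader who wants to know how such subjects fare off drug would go to the 5.3.3 tables and plots. As specified, these can show a centre at or near LLN without saying anything about that group.

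**Working it through.** **Plan figures.** The plan states no figure for the recovery analysis. Its nearest figures are in SAP section 4: 24% of 180 with at least one ALC <LLN by Week 48, 0.24 × 180 = 43.2, which matches its 43. I use N = 43 only as a convenient size; the number entering 5.3.3 is not given, nor is the share starting below 0.5.

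**Percent change.** Rise needed to reach LLN = 0.91/start − 1:

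- from 0.40: +128%
- from 0.49: +86%
- from 0.79: +15%
- from 0.85: +7%
- from 0.90: +1%

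So 0.40 to 0.60 is +50% and not recovered, while 0.88 to 0.95 is +8% and recovered.

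**Two-value check.** Let k of 43 subjects stay at 0.40 and the rest be at 0.95.

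- k = 10: median 0.95, Q1 0.95, mean (10 × 0.40 + 33 × 0.95)/43 = 0.82, minimum 0.40. Split by starting depth: <0.5 band median 0.40, 0/10 at LLN; the others 0.95, 33/33 at LLN.
- The median stays at or above 0.91 up to k = 21 of 43 (14 of 29, 9 of 20).
- Q1 falls below 0.5 only from k = 12 of 43 (28%).

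**Spread values, exact.** Assume severe starts uniform on 0.30–0.50, other starts uniform on 0.50–0.91, and others rising 40%, to 0.70–1.274. A severe rise of 0% or 20% leaves every severe value at or below 0.60, so the severe subjects fill the lowest ranks.

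- 20% severe: the pooled median is the (50 − 20)/80 = 37.5th percentile of the others, 0.70 + 0.375 × 0.574 = 0.915. Q1 is their 6.25th percentile, 0.736.
- 10% severe: median 0.70 + (40/90) × 0.574 = 0.955; Q1 0.70 + (15/90) × 0.574 = 0.796.
- 30% severe: median 0.70 + (20/70) × 0.574 = 0.864. Q1 now lies in the severe group: 0.47 with no severe rise, 0.56 with 20%.

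At 10% and 20% severe, neither statistic depends on whether the severe group rises 0% or 20% (its own median is 0.40 or 0.48, none at LLN). If 20% were severe and all of them recovered to the distribution of the others, the median would be 0.70 + 0.5 × 0.574 = 0.987, against 0.915: above LLN either way.

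**Sensitivity to the assumed 40%.** With 20% severe the median is (1 + r)(0.50 + 0.375 × 0.41) = 0.654(1 + r): 0.85 at r = 30%, 0.88 at 35%, reaching 0.91 only at about 39%. With 10% severe it is 0.682(1 + r): 0.89 at 30%, reaching 0.91 at about 33%.

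**Simulation** (N = 43, 5,000 repeats; severe starts 0.25–0.50, staying below 0.5; others ending uniform on 0.80–1.30). Probability that the pooled median is at or above LLN:

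| k severe | 8 | 10 | 13 | 17 | 20 |
|---|---|---|---|---|---|
| probability | 0.99 | 0.96 | 0.80 | 0.30 | 0.03 |

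**Later visits.** The extra follow-up ends once ALC reaches LLN, and SAP 5.1 imputes nothing. In the two-value setting, if 75%, 50%, 25% or 10% of recovered subjects still supply a value, the largest k that leaves the median at or above LLN is 18, 13, 8 or 3 of 43. Masking is therefore mainly an early-visit problem.

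**The case against.** The strongest reply is that low values would not be invisible. SAP 5.1 tables give the minimum and maximum, 5.4.2 lists hematology by subject, and 5.4.6 summarises or lists hematology in the follow-up period. That stands, and it rules out any claim that the outputs would show everyone recovered. But none of these ties a low value to the count at stopping, so none answers how the <0.5 starters fared. The option of additional analyses is not a specified summary.

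The illustrations also rest on chosen inputs. The 40% rise has no source, and with 20% severe a rise of 30–35% already puts the median below LLN. If subjects withheld for lymphopenia were half the pool or more, the median would fall to their level. Ending extra visits at LLN works the same way at later visits. These points limit how often the median would exceed LLN. They do not remove the main fault: the pooled figure cannot be interpreted without the mix of starting depths.

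Three stronger readings do not hold:

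- A reader might infer that the trial will report recovery where there is none. The documents give no share starting below 0.5, so this cannot be predicted.
- A reader might infer that recovery from <0.5 is the chief purpose of the follow-up. Neither document says so; 5.3.3 is descriptive and outside the stated primary and secondary endpoints.
- A reader might infer that 96-week completers will swamp the 4-week row, because 5.3.3 starts the period at the treatment end date. Its opening sentence covers only subjects who withhold or discontinue. The wording is unclear, and the plan's Week 48 counts cannot size the effect at Week 96.

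Parts of the SAP after 5.4.6 are redacted, so a stratified version there cannot be excluded; none is visible in 5.3.3 or 5.4.6.

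**Conclusion.** The point holds as a weakness in what SAP 5.3.3 specifies. The pool runs from subjects withheld for persistent ALC <0.5 to subjects already at or above LLN when they stopped. Where <0.5 starters are fewer than half of those observed at a visit, the pooled median can sit at or near LLN whether or not they recover. Where they are under about a quarter, Q1 does not show it either. Percent change cannot be read as recovery without the starting depth.

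The conclusion rests on two conditions the documents do not settle: that <0.5 starters are a minority at the visit, and that the others have risen far enough to bring the median to LLN. It is strongest at early visits. It affects a descriptive, safety-relevant output, not the primary analysis, and is worth correcting because the SAP already separates by ALC depth elsewhere.

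**What to change.** In SAP 5.3.3, present the ALC follow-up tables and figures, and those for selected subsets and Ig isotypes, by ALC at the follow-up baseline: <0.5, 0.5 to <0.8, 0.8 to <0.91, and ≥0.91 × 10^9/L. The last band is needed because the entry rule admits such subjects. The cut-points are those of 5.3.1, applied here to the single value at stopping; the two deepest 5.3.1 groups also require at least six months' duration, and the text should state the difference.

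For each band and visit, give n and the number and percent at or above LLN, with the denominator stated, since recovered subjects may have no later extra visits. Plot individual lines where cells are small. Keep the pooled version as supplementary. State whether 96-week completers enter through the treatment end date; if they do, show them separately.

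The cost is SAP wording and a few more descriptive panels from data already being collected, with no change to trial conduct. The downside is small cells, especially in the <0.5 band.
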